8.6 Follow-up Procedures

Additionally, to determine the safety and efficacy of using riboflavin-ultraviolet light induced collagen cross-linked cornea tissue in promoting retention, follow-up visits will be scheduled at Day 1 and 7 (± 3 days), week 4 (± 3 days), week 16 (± 2 weeks), week 24 (± 3 weeks), week 36 (± 3 weeks), and week 52 (± 4 weeks). Following week 52 visit, standard of care visits will occur every six months. The study will continue to collect data from these standard of care visits (post week 52 visit) in order to monitor subject safety for an additional 3 years or until study closure. Any procedures/exams performed during these visits will be standard of care and the MD will decide which procedures/exams are needed. Study staff will collect data for any procedures/exams that may be conducted as they pertain to the study (changes in medical history and medication prescription; BCVA, slit-lamp exam, IOP, funduscopy/B-Scan, OCT images, slit lamp photography and review of potential adverse events).

A description of imaging procedures follow in this section and a table of follow-up procedures organized by time-point can be found in section 7.7 below.

Cornea Thickness as measured by AS-OCT

Because corneal thinning will be used as a secondary endpoint and is an indication of corneal melts, cross- sections of the cornea will be obtained using anterior segment AS-OCT. This non-contact high-resolution imaging modality provides cross-sectional images of the cornea and anterior segment with a resolution of approximately 5-18 μ m. To evaluate the cornea, cross-sectional OCT images will be obtained at 0, 45, 90, 135, 180, 225, 270, 315 and 360 degrees.

Slit Lamp Photography

Because it is possible that slit lamp findings may be predictive of keratoprosthesis loss or corneal thinning, digital corneal photography will be done using a slit-lamp with a digital camera attachment and a flash-through-the-slit illumination system. By fine focusing on the surface of the cornea prior to corneal transplant surgery at the screening visit, and at Week(s) 1, 4, 16, 24, and 52, the photographer will capture the entire cornea using diffuse illumination and 10x magnification. If lids are drooping, the photographer will attempt to gently remove them from area of focus with a cotton swab.

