8.8 Early Termination

Subjects have a right to withdraw from the study at any time. Additionally, the subject may be withdrawn from the study for any reasons: if it is in the best interest of the subject, intercurrent illness, adverse events, or worsening condition. The site investigators or Medical Monitor may request the withdrawal of a subject because of protocol violations, administrative reasons, or any other valid and ethical reasons.

Reasons for subject termination may include, but are not limited to, the following:

- Investigator determination that it is not in the best interest of the subject to continue participation
- Serious adverse events

- Any other safety concerns

In the event of an adverse event in the study eye that is considered by the investigator or Research Monitor to be severe in intensity, the donor tissue will be removed and replaced with fresh cadaveric human cornea donor tissue with or without a keratoprosthesis, discontinuing the patient from further participation in the study.

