11.3 Sample Size Determination

To determine the number of subjects to enroll, we performed sample size calculations based on a review of keratoprosthesis retention rates from prior studies and conservative estimates of efficacy in the treatment arm. For the control arm, we used twelve-month retention rates ranging from 50 to 60%, which has been reported in autoimmune eyes at high risk for keratoprosthesis loss. Therefore, we anticipate the twelve month retention rate for the untreated (not cross-linked) cornea will be 50-60%. To estimate the retention rate in the treatment arm, we reviewed the retention rates from the two published case reports that describe cross-linking of the keratoprosthesis carrier cornea in high-risk eyes (Kanellopoulos et. al. & Robert). While the two case reports describe a 100% retention rate in a total of 12 eyes at one year, the exact retention rate for a multicenter study is not known. Using a two-sided log rank test for equality of survival curves, we performed sample size calculations so that we could detect a 30% difference in retention rate between the treatment group and the control group and specified the probability of type 1 error of 0.05, a study power of 80%, a follow up period of twelve-months, and a 4% loss to follow up. In order to detect a difference between the control arm and the treatment arm using

these considerations, the calculations resulted in sample size estimates between 82 and 88 subjects (Table 2). For practical purposes, we also took into consideration the time available for the study and the number of high risk keratoprosthesis procedures performed at each study site. Using the mid-range estimates, we aim to enroll 84 subjects into this study.

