11.4 Analysis Population

N/A

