### Previous KPro

- Previous KPro in the study eye: yes/no
  - If yes, how many, how long were they in the eye for and why were they removed.
  - We don't have exact dates for all previous ones since some were done at other hospitals.

Reorganize the primary and secondary outcome measures into:

- Efficacy endpoints:
  - Removal or not of the study KPro
  - Rate of retention at 52 weeks
  - Time from KPro study surgery to ocular surgery done to address a melt, including partial graft

- Safety endpoints:
  - Incidence of delayed epithelial healing at day 30 (week 4 visit)
  - Time from surgery to retroprosthetic membrane treatment (laser or surgical interventions)
  - Time from surgery to occurrence of vitritis (sterile or infectious)

We will conduct an initial analysis to examine if distributions of baseline characteristics are balanced between the two treatment groups in our randomized study. Standard descriptive statistics will be reported, median (min-max) for numerical variables and frequency count (%) for categorical variables. Comparisons of numerical characteristics between treatment groups will be conducted using the Mann-Whitney U- test. Comparisons of categorical characteristics will be conducted using Chi-square, or Fisher's exact test as appropriate.

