#### Primary Analysis

The primary efficacy analysis will follow an intent-to-treat analysis strategy including all randomized eyes. The major goal of this study is to determine the efficacy of using a collagen cross-linked cornea as a carrier for the Boston Keratoprosthesis in preventing corneal melts and increasing the retention of the keratoprosthesis.

The primary endpoint of the efficacy analysis is time from surgery to device loss or replacement. Kaplan-Meier event free survival by treatment groups will be determined by the product-limit method and compared by the log-rank test to examine if survival curves are significantly different between groups. In addition, we will use a Cox proportional hazards regression model to test the effectiveness of using a collagen cross-linked cornea as a carrier for the Boston Keratoprosthesis in preventing corneal melts and increasing the retention of the keratoprosthesis. We will obtain an estimate of the hazard ratio of device loss comparing treatment with control with 95% confidence interval (95% CI). This framework allows for adjustment of baseline covariates, which may be unbalanced by chance despite the randomization of treatment assignment. The proportional hazards assumption will be assessed by examining scaled Schoenfeld residuals and log-log plots, with testing done using the “stphtest” and “stphplot” functions in Stata (version 16.0; StataCorp LLC, College Station, Texas).

If Kaplan-Meier plots of event free survival by study time, or related plots of log (-log) (survival) indicate violations of the proportional hazards assumption, then a weighted log-rank test will be used according to strategies described by Peckova and Fleming.

We will further characterize the effectiveness of using a collagen cross-linked cornea as a carrier for the Boston Keratoprosthesis by creating a composite endpoint that captures survival time until KPro removal or ocular surgery to address a melt. We will calculate the survival time of the latter by choosing the date of whichever of these two happened first as the endpoint. In doing so, we will better capture the effectiveness of using the collagen cross-linked corneas as carriers for the KPro in preventing corneal melts even for those subjects in which the melt did not warrant KPro replacement.

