#### Secondary Analysis

We plan to conduct a number of pre-specified analyses of secondary study endpoints. Analyses of secondary “time-to-event” type endpoints (time to retroprosthetic membrane treatment and time to

occurrence of vitritis) will use the Kaplan-Meier approach with log-rank test and Cox proportional hazards regression, similar to the primary analysis for time to device loss.

Comparison of cornea thickness metrics at week 1, 4, 16, 24, and 52 for treatment versus control group will be performed using the Mann-Whitney Wilcoxon test at each time point.

Furthermore, a mixed model regression analysis using generalized estimating equations (GEE) with compound symmetry covariance structure for repeated measures will be used to examine the effect of time, treatment and the interaction between them on cornea thickness to evaluate the change over time between and within the treatment groups. Comparison of twelve-month retention rate and incidence of delayed epithelial healing at Day 30 (week 4 visit) between groups will be performed using Chi-square test, or Fisher's exact test as appropriate.

In addition, the occurrence of any adverse events will be described and compared between treatment arms of the study.

We will run multivariable analysis with relevant information from the subject's ocular history to determine if certain characteristics inform or predict the loss of the study KPro or the survival time between insertion and removal. Among these, we will include age at study surgery, sex, race and whether patients- had previous KPros in the study eye and, if so, how many. For the subset of patients who did have previous Kpros in the study eye, we will look at the survival time of the one immediately before the study eye and compare it to the survival time of the study one. We will compare mean duration for these and analyze if there is a statistically significant difference among those who received a collagen cross-linked carrier cornea versus those who did not.

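### Twelve-month retention (secondary) is compared by chi-square or Fisher with no rule for eyes censored before week 52; the week-52 Kaplan-Meier estimate is a cheap improvement (minor)

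*SAP*

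**What the plan says.** The SAP (Secondary Analysis) and Protocol 11.5 use the same sentence: "Comparison of twelve-month retention rate and incidence of delayed epithelial healing at Day 30 (week 4 visit) between groups will be performed using Chi-square", or Fisher's exact test. The SAP's regrouped endpoint list (under Previous KPro) places "Rate of retention at 52 weeks" among the efficacy endpoints.

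Follow-up can end early. Protocol 8.8 says "Subjects have a right to withdraw from the study at any time", and it also lets subjects be withdrawn for adverse events or a worsening condition. The sample size in Protocol 11.3 assumes "a follow up period of twelve-months, and a 4% loss to follow up".

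Protocol section "11.4 Analysis Population" is marked not applicable. The intent-to-treat statement is confined to the primary analysis: "The primary efficacy analysis will follow an intent-to-treat analysis strategy including all randomized eyes". The SAP's Inclusion Criteria table removes one subject from efficacy analysis. None of these texts says what week-52 status to give an eye that was not followed to week 52.

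Kaplan-Meier curves of time to device loss are already planned in both documents. Protocol 8.6 puts the week-52 visit within ±4 weeks and adds: "The study will continue to collect data from these standard of care visits (post week 52 visit) in order to monitor subject safety".

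**The concern.** Retention at twelve months is a point on a survival curve, and some eyes will be censored before that point. A chi-square or Fisher test cannot use a censored eye until someone decides that it was retained, that it failed, or that it leaves the table. The plan does not make that decision.

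If censoring is unrelated to device loss, counting these eyes as retained biases retention upward. Dropping them, or counting them as failed, biases it downward. If eyes tend to be withdrawn shortly before the device would be lost, dropping them can bias retention upward instead.

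The reported rate in each arm therefore depends on an unwritten choice. It can also disagree with the week-52 point on the Kaplan-Meier curve in the same report. The SAP already gives pooled results (68 eyes, 20 removals), so a rule left open now would be chosen after some outcome information is known.

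**Working it through.** **Inputs.** Retention of 55% (control) and 85% (treated) is the middle row of the sample-size table in Protocol 11.3; the 4% loss is from the same section. The 68 eyes are from the SAP's preliminary results. Assumptions: 34 eyes per arm (the split is not given), exponential time to device loss, dropout uniform over 52 weeks, equal in both arms and unrelated to device loss. Seven censored eyes is an illustration.

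**The plan's own figure.** The hazard ratio is ln 0.85 / ln 0.55 = 0.272. Freedman's formula gives (1.960 + 0.842)² × [(1 + 0.272)/(1 − 0.272)]² = 23.9, so 24 events. N = 24 / 0.30 / 0.96 = 83.3, so 84, as stated. The other two rows give 90 and 80 against 88 and 82. The planned rates are thus a sound basis, and the sample size belongs to the log-rank test, not to this comparison.

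**Bias under each rule.** Let p be true week-52 retention and d the dropout probability.

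- Share censored with the device in place: c = d(1 − p)/(−ln p). The multiplier of d is 0.7527 at p = 0.55 and 0.9230 at p = 0.85.
- Counted as retained: (1 − d)p + c
- Dropped: (1 − d)p/(1 − c)
- Counted as failed: (1 − d)p

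At d = 0.04, c is 3.01% in control and 3.69% in treated:

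| Rule | Control % | Treated % | Difference | Bias (points) |
|---|---|---|---|---|
| Retained | 55.8 | 85.3 | 29.5 | -0.5 |
| Dropped | 54.4 | 84.7 | 30.3 | +0.3 |
| Failed | 52.8 | 81.6 | 28.8 | -1.2 |

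For 7 of 68 eyes censored, d × (0.7527 + 0.9230)/2 = 7/68 gives d = 0.123. Then c is 9.25% and 11.34%, or about 3.1 and 3.9 eyes:

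| Rule | Control % | Treated % | Difference | Bias (points) |
|---|---|---|---|---|
| Retained | 57.5 | 85.9 | 28.4 | -1.6 |
| Dropped | 53.2 | 84.1 | 30.9 | +0.9 |
| Failed | 48.2 | 74.6 | 26.3 | -3.7 |

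**Scale.** The standard error of the difference is √(0.55 × 0.45/34 + 0.85 × 0.15/34) = 10.5 points. The largest bias is 1.2/10.5 = 0.11 standard errors at 4% dropout, and 3.7/10.5 = 0.35 with seven eyes censored. Single-arm rates move more: in the second table, 9.3 points in control and 11.3 in treated between the extreme rules.

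**Informative withdrawal.** If 20% of eyes about to fail are withdrawn just before the loss, the Kaplan-Meier estimate tends to p^0.8: 0.62 where the truth is 0.55, and 0.88 where it is 0.85. If 4% of eyes are censored and all were about to fail, dropping them gives 0.55/0.96 = 57.3% (+2.3 points) and 0.85/0.96 = 88.5% (+3.5 points).

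**Power and error rate.** These come from 10,000 simulated trials with 34 eyes per arm and 7 of 68 censored, the censored share being equal in both arms. Power at 55% versus 85% is about 74% for the Kaplan-Meier difference with complementary log-log limits, and 76-77% for chi-square/Fisher with censored eyes retained or dropped. With 55% in both arms, rejection rates are 4.7% for Kaplan-Meier and 5.2%, 5.3% and 4.3% for retained, dropped and failed.

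**The case against.** The strongest reply is that one sentence giving a rule for the existing test, with best- and worst-case bounds, would close the gap. Replacing the method turns the protocol-specified test into a sensitivity analysis after pooled results have appeared in the SAP, and it gains no power. Those costs are real. However, each simple rule is biased even when censoring is harmless, whereas the Kaplan-Meier estimate is then unbiased and already planned. The bounds are kept in the fix.

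It can also be said that the SAP partly defines the efficacy population by removing one subject, and that intent-to-treat could be read across. That stands, but it settles who is counted, not the status of an eye that was not observed at week 52.

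Three stronger readings are tempting, and the documents do not support them:

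- That Kaplan-Meier removes the problem altogether. It does so only if censoring is unrelated to impending loss, and Protocol 8.8 allows withdrawal for a worsening condition.
- That the chi-square/Fisher test would give false positives. With equal dropout, none of the three rules raises the error rate materially.
- That unequal dropout distorts the result badly. At 5% control and 15% treated dropout, the failed rule would give 0.85 × 85% − 0.95 × 55% = 20.0 points instead of 30. But the documents report no dropout by arm, and the trial is double-masked, so this remains hypothetical.

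**Conclusion.** The point holds as a minor, cheap improvement. Both documents compare a censored quantity with a test that needs complete week-52 status, and neither says how incomplete eyes are counted.

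At the planned 4% loss the effect on the arm difference is at most about 1.2 points. With an assumed seven censored eyes it is at most about 3.7 points, or 0.35 of a standard error. These figures rest on equal dropout, dropout unrelated to device loss, exponential loss times, 55% versus 85% retention and 34 eyes per arm. The actual number censored before week 52 is not given.

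A reader might infer that the trial's main efficacy conclusion is at risk. It is not: the endpoint is secondary, and the primary log-rank and Cox analysis handles censoring.

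**What to change.** In the SAP's Secondary Analysis, and in Protocol 11.5 or as a documented deviation from it, replace the retention part of the sentence with the following:

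- Report twelve-month retention per arm as the Kaplan-Meier estimate at 52 weeks from surgery, with a 95% confidence interval on the complementary log-log scale. Give the difference with a 95% interval, for example by combining the two arm intervals (square-and-add).
- If an arm has no loss by week 52, use an exact bound based on the eyes still at risk at week 52.
- Count a removal before week 52 as an event, although it ends participation (Protocol 6.8 and 10.3). Otherwise, count an eye seen with the device in place at an in-window week-52 visit (±4 weeks) or at any later visit as retained at week 52.
- Report the number of eyes censored before week 52 by arm.
- Keep chi-square/Fisher as a sensitivity analysis, run with all censored eyes retained and again with all failed.

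The comparison of epithelial healing is unchanged.

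The cost is one rewritten sentence in each document (or a recorded deviation) and one count per arm. No new data are needed, since the curves are planned and later visits are collected. The downside is that the protocol-specified test becomes secondary to the estimate, with no gain in power.

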2. STUDY OBJECTIVES

2.1 Primary Objective

This is a phase I/II prospective, randomized, multicenter, double-masked, vehicle-controlled clinical trial evaluating the safety and efficacy of corneal collagen cross-linking the keratoprosthesis carrier tissue in subjects who are candidates for high-risk keratoprosthesis implantation because of a history of corneal melts, sterile corneal ulcers, or autoimmune diseases (e.g., Stevens-Johnson syndrome, ocular cicatricial pemphigoid).

Objective 1:

Determine the safety of using a collagen cross-linked cornea as a carrier for the Boston Keratoprosthesis in subjects who are at high risk for corneal melts and are not candidates for a standard corneal transplant.

Objective 2:

Determine the efficacy of using a collagen cross-linked cornea as a carrier for the Boston Keratoprosthesis in preventing corneal melts and increasing the retention of the keratoprosthesis. This will be tested using the outcome measures listed in section 10.

2.2 Secondary Objective(s):

N/A

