Eighty-four subjects will be randomized equally to treatment or control group. Randomization will be stratified by 16 centers, as well as two pre-operative diagnostic categories: autoimmune disease vs. prior corneal melt without autoimmune disease. Eye with a history of autoimmune disease may have a different risk of a new melt than eye that have a history of a prior corneal melt. Thus there will be a total of 32 strata. Stratification will ensure balance of the stratification factors between the two arms of the study. A number of blocks of varying size will be determined (e.g. 5 blocks of size 4, 6 blocks of size 2) and randomization assignments will be prepared accordingly. Since we have 32 strata, relatively small block sizes will be planned to minimize the chance of large departures from the desired allocation ratio that could occur due to incomplete blocks by the time of completion of patient recruitment. Although the ability of the clinical staff to predict future treatment assignments is increased due to smaller block sizes, we do not think that this will be a major issue for the present study.

Retention Rate for Control Group	Retention Rate for Treatment Group	Total Sample Size
0.50	0.80	88
0.55	0.85	84
0.60	0.90	82

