### Inclusion Criteria:

Previous sterile corneal ulceration	56
Autoimmune disease (ocular or other)	15
Ocular Cicatricial Pemphigoid	1
Steven Johnson's syndrome	7
Rheumatoid Arthritis	4
GVHD	2
Vogt-Koyanagi-Harada	1
Both autoimmune disease and previous ulceration	4
No autoimmune disease or previous ulceration	1

\*Will include this subject for safety analysis but will remove for efficacy analysis

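### Delayed epithelial healing gets a test but no effect estimate, and the adverse-event comparison is unspecified; with about 34 eyes per arm, a non-significant p would not bound harm

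*SAP*

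**What the plan says.** Safety comes first among the protocol's objectives (section 2.1, Objective 1): "Determine the safety of using a collagen cross-linked cornea as a carrier for the Boston Keratoprosthesis". No numerical criterion is attached to it.

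The SAP, under the heading Previous KPro, sorts the outcomes into efficacy and safety endpoints. Three are listed as safety endpoints. One is binary: "Incidence of delayed epithelial healing at day 30 (week 4 visit". The other two are times to event: retroprosthetic membrane treatment and vitritis.

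The SAP's Secondary Analysis section then treats them differently:

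- **Delayed epithelial healing:** comparison of "incidence of delayed epithelial healing at Day 30 (week 4 visit) between groups will be performed using Chi-square test", with Fisher's exact test as the alternative. Protocol section 11.5 says the same. Neither document adds an effect measure, an interval or a margin.
- **Adverse events:** "the occurrence of any adverse events will be described and compared between treatment arms of the study". No test, effect measure or interval is named. Protocol sections 9.1 and 11.6 add incidence, severity and relatedness summaries. Section 9.1 also names three ocular events of special interest: infectious keratitis, a positive fungal rim culture and retinal detachment.
- **Membrane treatment and vitritis:** Kaplan-Meier, log-rank and Cox regression on the model of the primary analysis, for which the SAP plans a hazard ratio with a 95% CI.

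**The concern.** An equality test asks whether the data are incompatible with no difference. A safety objective asks how much excess harm the data still allow. In a small trial these questions can have very different answers, because a p-value above 0.05 is compatible both with no harm and with a large increase in harm.

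The trial's size comes entirely from the retention endpoint (protocol section 11.3), so nothing in the plan ensures useful precision for a binary safety outcome. If the report gives only two percentages and a p-value for delayed healing, and an undefined comparison for infectious keratitis or retinal detachment, the reader cannot tell whether a doubling has been excluded. The plan already supplies a hazard ratio with an interval for efficacy and, by analogy, for the two time-to-event safety endpoints. The binary safety outcomes are where that is missing.

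**Working it through.** **Inputs from the documents**

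- Eyes: 68 (opening of the SAP). The one ineligible subject stays in the safety set: "Will include this subject for safety analysis but will remove for efficacy analysis".
- Allocation: "Eighty-four subjects will be randomized equally to treatment or control group". This gives about 68/2 = 34 per arm. The actual arm sizes are not stated, so 34 is inferred.
- Significance level: the sample-size section "specified the probability of type 1 error of 0.05" and is two-sided ("Using a two-sided log rank test for equality of survival curves"). No level is given for safety comparisons; two-sided 0.05 is assumed.

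**Assumed, because the documents give no figure:** the control-arm rate, taken over 5–30%, and the harm of interest, taken as a doubling.

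**The plan's own figure.** The plan states no power or precision for safety. Its only calculation is for retention. With HR = ln(S_t)/ln(S_c) and Freedman's events formula (1.96 + 0.842)² × [(1 + HR)/(1 − HR)]², 0.55 against 0.85 gives HR = 0.272 and 24 events. Then 24/0.30 = 80 eyes, or 40 per arm, and 40/0.96 rounds up to 42 per arm, total 84, as stated. The other two rows give 90 (stated 88) and 80 (stated 82), which is close. The size therefore follows from retention alone.

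**Step 1: chance of missing a doubling.** For control rate p, sum Bin(a; 34, p) × Bin(b; 34, 2p) over all pairs (a, b) whose two-sided p-value is at least 0.05. The mixed rule uses Fisher when any expected count is below 5 and chi-square otherwise.

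| Control v treated rate | Fisher | Chi-square, uncorrected | Mixed rule |
|---|---|---|---|
| 5% v 10% | 97.2% | 87.7% | 96.9% |
| 10% v 20% | 87.8% | 78.4% | 82.6% |
| 15% v 30% | 77.7% | 67.1% | 67.4% |
| 20% v 40% | 65.9% | 54.5% | 54.5% |
| 25% v 50% | 50.7% | 40.9% | 40.9% |
| 30% v 60% | 37.8% | 29.6% | 29.6% |

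At the planned 42 per arm, Fisher would still miss 82.5% (10% v 20%) and 56.4% (20% v 40%). By the usual two-proportion formula, 80% power for a doubling needs 199 per arm from 10%, or 82 per arm from 20%.

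**Step 2: what an interval would show.** Newcombe's interval combines the Wilson limits of each arm. For 7/34 = 0.2059 the Wilson limits are 0.1035 and 0.3680. With 7/34 in both arms the difference is 0 and the half-width is √[(0.2059 − 0.1035)² + (0.3680 − 0.2059)²] = √(0.01048 + 0.02628) = 0.192. The 95% CI is −19.2 to +19.2 points.

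For 3/34 control against 7/34 treated, the difference is 11.8 points with a 95% CI of −5.7 to +29.0. The p-value is 0.30 (Fisher) or 0.17 (chi-square), and it conveys none of that range.

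For a rare event of special interest, zero events in 34 eyes leaves a one-sided 95% upper bound of 1 − 0.05^(1/34) = 8.4%.

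**The case against.** The strongest reply has five parts.

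1. **Adverse events are not analysed by significance tests alone.** This stands. The SAP says they are described as well as compared and names no test, and the protocol plans summaries of incidence, severity and relatedness. The gap there is an unspecified comparison without an interval.
2. **The miss rate depends on a control rate the documents do not give.** This stands. At 25% or 30%, chi-square detects a doubling more often than not. Protocol section 9.2 lists epithelial defects among expected early complaints. That is not a rate of delayed healing at day 30, but it lends no support to assuming a low rate. The 66–88% figure is Fisher at 10–20% and must be read with that condition.
3. **Two of the three listed safety endpoints already have Cox models.** This stands. A reader might infer that Objective 1 rests wholly on bare p-values; the documents do not support that.
4. **Nothing in the plan says p ≥ 0.05 will be taken as evidence of safety.** This stands too. A reader might infer that intention, but protocol section 9.1 defines safety by the incidence of related adverse events, which is a descriptive basis. However, neither document says what result would count as safe, and a test reported alone leaves that open.
5. **Low power for safety is inherent in a phase I/II trial sized on retention, and an interval does not cure it.** This is true, but it does not answer the point. The interval is recommended because it makes that imprecision visible.

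There is also no need to delete a test that both documents specify; it can stay beside the interval.

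**Conclusion.** The point holds in a limited form. Delayed epithelial healing is a named safety endpoint with an equality test and no planned estimate or interval, and the adverse-event comparison is left undefined. With about 34 eyes per arm and an assumed control rate of 10–20%, a doubling goes undetected 66–88% of the time with Fisher and 54–78% with chi-square. Over 5–30% the range is about 97% to 30%. The interval result does not need an assumed true rate: at observed counts of 7/34 in each arm, an excess of up to 19 points remains open.

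This rests on equal arms, two-sided 0.05 and a doubling as the harm of interest. It does not show that the trial cannot address Objective 1, or that the sponsor will equate non-significance with safety. It is an inexpensive improvement that should be made, and it leaves the primary analysis untouched.

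**What to change.** In the SAP's Secondary Analysis section, and in protocol section 11.5 for consistency:

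- For delayed epithelial healing at day 30 and for each of the three ocular adverse events of special interest in protocol section 9.1, make the risk difference (cross-linked minus control) with a 95% CI, for example Newcombe's, the main reported result, with counts and denominators by arm.
- Keep the chi-square or Fisher p-value only as a supplement.
- Word the safety conclusion by the largest excess risk that the upper confidence limit leaves open, and state that a non-significant p-value is not evidence of safety.

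The cost is a few sentences of SAP text and one table column. It needs no new data. The real downside is that the safety statement will read less favourably, because at this size the upper limits will be wide.
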